4.4 Analysis populations

4.4.1 Intention-to-treat populations

Intention-to-treat (ITT) populations include all patients who undergo randomization and are characterized by the treatment they were randomized to receive (Immediate Results vs. Delayed Results).

4.4.2 Complete case populations

The complete case populations consist of patients who undergo randomization and complete all study assessments, including both the baseline and end-of-study patient surveys and end-of-study LDL-C measurement.

4.4.3 Subgroup populations

Additional subgroups of the study population may include the analyses of patients stratified by demographic (e.g. age), sex, or baseline LDL-C values. Each subgroup population will be described in detail as reported in the final study manuscript(s).

4.5 Baseline patient characteristics

Baseline characteristics will be summarized and presented for participants in the ITT populations. Standard statistical summaries, depending on data type and distribution, will be presented as 1) total numbers of participants with each characteristic (n) and as a proportion (%) of each group stratified by randomization arm or 2) as means and standard deviations (if normally distributed) or medians and interquartile ranges (IQR) (if non normally distributed) stratified by randomization arm. No statistical testing will be carried out for participant baseline characteristics or measures between treatment groups.

At minimum, the below participant baseline characteristics, including the pre-specified baseline measurements of the study outcomes described in Section 6.0, will be derived and reported:

| Baseline characteristic | How derived | Presentation |
|---|---|----------------------------------|
| Age in years | As calculated using EHR administrative data relative to date of consent and enrollment. | mean (SD) / median (IQR) |
| Gender / Sex | As determined by EHR administrative data. | n (%) |
| Race | As determined by EHR administrative data and/or data collected from baseline survey. | n (%) |
| Ethnicity | As determined by EHR administrative data and/or data collected from baseline survey. | n (%) |
| Socioeconomic Status / Area Deprivation Index | Calculated using income, geographic, and other EHR administrative data.(ADI) ⁹ | n (%) |
| Self-reported health status and quality of life | As determined by data collected from baseline survey. (VR-12) ¹⁰⁻¹² | mean (SD) / median (IQR) |
| Self-reported patient activation | As determined by data collected from baseline survey. (PAM-13) ¹³ | mean (SD) / median (IQR) / n (%) |
| Beliefs about medications | As determined by data collected from baseline survey. (Beliefs About Medicines Questionnaire) ¹⁴ | mean (SD) / median (IQR) |
| Low-density lipoprotein cholesterol | As determined by EHR data. | mean (SD) / median (IQR) |
| Lipid-lowering pharmacotherapy | As determined by data collected from baseline survey and EHR data. | n (%) |

5.0 Statistical Considerations

5.1 Statistical framework

The principal analysis uses an intention-to-treat (ITT)¹⁵ approach to compare the Immediate Results and Delayed Results arms. Using an independent t-test, analysis of the primary outcome uses a t-statistic, and two-sided type I error rate of 0.05 to test the null hypothesis of no difference in LDL-C change between arms. To quantify the treatment arm difference for the primary endpoint, a mean difference will be presented with a corresponding confidence interval estimate. Mean change in LDL-C is also reported separately for each arm. Similarly, for secondary and other pre-specified outcomes an ITT approach is used to make outcomes comparisons across treatment groups. Subset analyses, including sensitivity and group analyses by demographic, variant confirmation status, or other study or patient characteristics, are considered exploratory and will be described in detail if reported.

5.2 Interim analyses

No formal interim hypothesis testing is planned.

5.3 Timing of final analyses

Final analyses of the MVP-ROAR-FH Study data are conducted upon the conclusion of the final participant's data collection procedures (*i.e.*, end-of-study survey and biospecimen collection).

5.4 Confidence intervals, *P* values, and multiple testing

All statistical testing is reported with an effect, a two-sided 95% confidence interval, and *P* value, unless otherwise specified. *P* values less than 0.05 will be reported as significant for the primary outcome. *P* values reported as significant for secondary outcomes will undergo Bonferroni correction for multiple hypothesis-testing. Other pre-specified and post-hoc analyses are considered exploratory.

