3.2 Sample size

The MVP-ROAR-FH Study aims to enroll ten participants into a pilot trial and 244 participants into the RCT.

Sample size is based on the primary outcome of change in LDL-C in each arm after 6 months. Assuming a mean LDL-C reduction of 20% in the Immediate Results arm, a mean LDL-C reduction of 0% in the Delayed Results arm, and a common standard deviation of 30%,² 72 total participants (36 per arm) are needed to have 80% power to detect a significant between-group difference at alpha=0.05. Enrollment of twice this number (144 total) will account for an absence of therapy escalation in up to 50% of participants in the Immediate Results arm. Enrollment of 180 total participants will account for up to 20% loss to follow-up.

| Change in LDL-C at 6 months | | | Total sample size required |
|-----------------------------|-----------------|-----------|----------------------------|
| Immediate Results | Delayed Results | Common SD | |
| -20% | 0% | 30% | 72 |
| -20% | 0% | 40% | 126 |
| -20% | -5% | 30% | 126 |
| -20% | -5% | 40% | 224 |

An important secondary outcome is the proportion of participants in each arm meeting accepted LDL-C targets at 6 months (<100 mg/dL for primary prevention and <70 mg/dL for secondary prevention). In preparatory-to-research analyses, only 175/322 (46%) MVP participants with a potentially pathogenic LDLR variant had a most recent LDL-C <100mg/dL. To have 80% power to detect a between-arm difference of 20% of participants meeting this LDL-C target at alpha=0.05, up to 194 total participants are needed (97 per arm). To account for up to 20% loss to follow-up, a total of 244 participants (122 per arm) are needed.

| Proportion of participants with LDL-C < 100mg/dL at 6 months | | Total sample size required |
|--|-----------------|----------------------------|
| Immediate Results | Delayed Results | |
| 10% | 30% | 124 |
| 20% | 40% | 162 |
| 30% | 50% | 186 |
| 40% | 60% | 194 |

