6.2 Secondary outcomes

6.2.1. Proportion meeting LDL-C targets

The proportion of participants meeting individualized clinically significant LDL-C targets (<100mg/dL for primary prevention and <70 mg/dL for secondary prevention) will be determined at 6 months, using the LDL-C values as described for the primary outcome in Section 6.1.

Secondary prevention will be defined as any patient with any of the following:

Pre-existing atherosclerotic disease (ASCVD): acute coronary syndrome in the prior 12 months, history of myocardial infarction, history of ischemic stroke, symptomatic peripheral artery disease including aneurysm, all of atherosclerotic origin.

Presence of any ASCVD risk factors: age ≥ 65 years; prior percutaneous coronary intervention; prior coronary artery bypass graft; other evidence of coronary artery disease; diabetes mellitus; hypertension; chronic kidney disease; current smoking; congestive heart failure; family history of premature ASCVD; elevated coronary artery calcium score, Lp(a), or apoB; or ankle-brachial index < 0.9 .

All other participants will be considered eligible for primary prevention.

The primary or secondary prevention status of each participant will be determined by clinician review of participant medical records through the end-of-study date. The clinician reviewer(s) will be blinded to randomization status. For each participant deemed eligible for secondary prevention, the clinician will record the reason(s) for eligibility in a study database.

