6.2.2. Intensification of pharmacotherapy

The proportion of participants with an intensification of lipid-lowering pharmacotherapy will be determined from baseline and end-of-study prescription data, obtained from the CDW, medical record review, and patient surveys. Intensification of pharmacotherapy at 6-months will be a composite outcome including prescription of new monotherapy, dose escalation of existing pharmacotherapy, or addition of one or more medications to existing pharmacotherapy compared to baseline pharmacotherapy status.

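### Section 5.4 uses single-step Bonferroni for two secondary outcomes without fixing the family; Holm keeps the same 5% familywise ceiling and is never less powerful

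*SAP*

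**What the plan says.** SAP section 5.4 sets the threshold for the primary outcome: P "values less than 0.05 will be reported as significant for the primary outcome". For the secondary outcomes it says that P "values reported as significant for secondary outcomes will undergo Bonferroni correction for multiple hypothesis-testing". It gives no number of tests, no adjusted threshold and no step-down rule. The same section plans unadjusted intervals for every test ("All statistical testing is reported with an effect, a two-sided 95% confidence interval") and classes the remaining analyses as exploratory.

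Section 6.2 holds exactly two secondary outcomes, headed "6.2.1. Proportion meeting LDL-C targets" and "6.2.2. Intensification of pharmacotherapy". The family of two can therefore be inferred, but section 5.4 does not state it.

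Section 3.2 uses the first of these outcomes to set enrolment: "at alpha=0.05, up to 194 total participants are needed (97 per arm"). It then inflates this to 244 (122 per arm) for 20% loss to follow-up.

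**The concern.** Two features of the sentence in section 5.4 deserve attention.

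The first is the choice of rule. Single-step Bonferroni tests each of the two outcomes at 0.025 whatever the other shows. Holm tests the smaller P value at 0.025 and, if that is significant, the other at 0.05. It cannot reject less than Bonferroni, and the 5% ceiling is the same. The outcome that may lose power is the one that fixed the size of the trial.

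The second is the wording. Attaching the correction to P values described as significant, with no divisor given, leaves open what the P value is multiplied by. A multiplicity rule should not need interpreting once results are known.

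**Working it through.** **Inputs.** From section 3.2: 40% vs 60% (the row of the table with the largest N), 80% power, alpha 0.05, 20% loss. From section 3.3: 1:1 allocation. From section 5.4: two-sided tests and Bonferroni. From section 6.2: two outcomes. Assumed, because the SAP gives no figures: the power of the intensification comparison, and a correlation of 0 to 0.5 between the two test statistics.

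**1. The plan's own figure.** With pooled variance under the null and no continuity correction,

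n per arm = [1.960 × √(2 × 0.5 × 0.5) + 0.842 × √(0.4 × 0.6 + 0.6 × 0.4)]² / 0.20² = 96.9, so 97 per arm and 194 in total.

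97 / 0.8 = 121.25, so 122 per arm and 244 in total. Both figures reproduce.

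**2. Power under Bonferroni.** Power = Φ{[0.20 × √n − z × √0.5] / √0.48}, with z = 1.960 at alpha 0.05 and z = 2.241 at 0.025.

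| Evaluable per arm, 40% vs 60% | alpha 0.05 | alpha 0.025 |
|---|---|---|
| 97 (20% lost) | 80.0% | 71.1% |
| 122 (none lost) | 88.3% | 81.6% |

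The other rows of the section 3.2 table are less demanding. At 97 per arm and alpha 0.025, power is 73% (30/50), 79% (20/40) and 90% (10/30).

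**3. Holm's error rate.** If both nulls are true, a false claim needs the smaller P value to be at or below 0.025. The chance of that is at most 0.025 + 0.025 = 0.05 under any dependence. If one null is true, a false claim needs that outcome's P value to be at or below 0.05, so the chance is again at most 0.05. Simulation with 1,000,000 pairs and correlation 0 to 0.7 agrees:

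- Both nulls true: 4.3% to 5.0%, identical for Bonferroni and Holm.
- One null true, the other outcome with 80% power at 0.05: 3.9% to 4.3% for Holm, 2.5% for Bonferroni.

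**4. Power for LDL-C targets under Holm, 97 per arm, 40% vs 60%.** Holm adds the cases in which the LDL-C P value lies between 0.025 and 0.05 and intensification is significant at 0.025. With independent tests,

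power = 0.711 + (0.800 − 0.711) × q,

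where q is the power of intensification at 0.025. For q = 0.80 this is 0.711 + 0.089 × 0.80 = 0.782. Simulation gives the values at other correlations.

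| Intensification power at 0.025 (assumed) | LDL-C target power under Holm, correlation 0 to 0.5 |
|---|---|
| no effect | about 71% |
| 30% | 72.5-73.7% |
| 50% | 74.2-75.5% |
| 80% | 77.5-78.2% |
| 90% | 78.8-79.1% |
| 95% | 79.5-79.6% |

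In each row the first figure of a range is at correlation 0.5 and the last at 0. The gain over 71% therefore runs from nothing to about 8 or 9 percentage points.

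**5. What the wording could mean.**

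- *Divisor fixed at two.* Keeping P values below 0.05 and then requiring 2P < 0.05 is the same as requiring P < 0.025, which is ordinary Bonferroni. Familywise error with independent tests is 1 − 0.975² = 4.9%.
- *Divisor equal to the number of significant results.* A lone P < 0.05 would be multiplied by 1. With independent tests, familywise error is 2 × 0.05 × 0.95 + (0.05² − 0.025²) = 0.0950 + 0.0019 = 9.7%. By simulation it is 9.4% at correlation 0.3 and 9.0% at 0.5.

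**The case against.** The strongest reply is that this is a preference between valid methods. Bonferroni over two named outcomes controls familywise error, nothing else in the SAP contradicts it, and Holm's advantage applies to any Bonferroni plan. That stands as far as validity goes. It does not answer why a rule that can only reject less should be kept when the change costs one sentence.

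The gain is also uncertain. It depends on an intensification effect for which the SAP gives no rates, and it vanishes if there is none. The 71% starting point is the hardest row of the table combined with the full planned loss. Both points are right, which is why the result is given as a range beside the more comfortable cases. The fall from 80% to 71% arises because the outcome was sized at 0.05 and is tested at 0.025; Holm recovers only part of it.

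Nor is Holm wholly free. Bonferroni has simple matching 97.5% intervals and Holm does not. With one true null, Holm's error is nearer the ceiling. The first matters little here, because section 5.4 reports unadjusted 95% intervals whichever rule is used.

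A reader might infer from the wording that a single significant secondary result would go uncorrected, with familywise error of 9 to 10%. The document does not support this. It never says that the divisor is the number of significant results, and its stated purpose of correcting for multiple hypothesis testing points to the hypotheses tested. Under that reading, the order of the words does no harm.

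**Conclusion.** The point holds as an inexpensive improvement, together with a gap in the wording. The planned Bonferroni correction is valid once the family is taken to be the two outcomes in section 6.2. Holm over the same two is at least as powerful in every case and has the same 5% familywise ceiling. In the least favourable planned case, power for LDL-C targets moves from 71% to between about 71% and 80%, depending on an assumed intensification effect. With full retention, power is adequate under either rule.

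The missing family and divisor are an ambiguity to close, not a demonstrated inflation of error. The primary outcome is not affected.

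**What to change.** In section 5.4, replace the sentence on secondary outcomes with: *The two secondary outcomes (LDL-C targets, intensification) form one family of m = 2 whatever their results and are tested by Holm at familywise 0.05: the smaller P against 0.025 and, if significant, the other against 0.05.* Date the amendment before unblinding.

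Add that the reported 95% intervals are unadjusted and may not match the adjusted decisions; this is true under either rule.

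The cost is one or two sentences, with no change to data collection, sample size or conduct. If the sponsor prefers Bonferroni, for instance to report matching 97.5% intervals, section 5.4 should still name the two outcomes and state the 0.025 threshold.

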5.5 Missing data

Prior to statistical analysis, outcomes data are reviewed for the amount and pattern of data missingness (*e.g.*, missing at random) using standard statistical software and methods. For outcomes analysis, partially observed outcomes may be imputed using mean or median imputation, multiple imputation, or comparable methods, as appropriate.¹⁶⁻¹⁸ Any necessary imputation will be conducted separately within each treatment arm. Proportions of data missingness, reasons for missingness (if known), and methods used for data imputation if required, including number of imputations and sensitivity analyses performed, will be reported in the final manuscript(s).

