7.2 Primary outcome

The difference in LDL-C reduction after 6 months between the Immediate Results arm and the Delayed Results arm will be assessed. The LDL-C values at baseline and 6 months will first be summarized descriptively for each arm. The change in LDL-C from baseline to 6 months will be calculated for each participant. An independent *t*-test will be employed to compare the mean LDL-C change between the two arms, assuming normally distributed data. If the change scores do not follow a normal distribution, a non-parametric alternative, the Wilcoxon rank-sum test, may be used. The effect size (Cohen's *d*), confidence intervals, and *P* value will be reported to determine the statistical significance of the observed difference. Additionally, potential confounders may be included in regression modeling to ensure the robustness of findings.

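### Section 5.5 permits single mean or median imputation of tested outcomes, which makes the standard error too small and pushes the type I error above 5%

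*SAP*

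**What the plan says.** Section 5.5 of the SAP provides that "partially observed outcomes may be imputed using mean or median imputation, multiple imputation, or comparable methods, as appropriate", and that "Any necessary imputation will be conducted separately within each treatment arm". No outcome is exempted and no rule is given for choosing among the methods. The choice follows a review of the outcome data. The method used, the number of imputations and any sensitivity analyses are to be reported in the manuscript.

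The primary analysis is an unadjusted comparison: "An independent *t*-test will be employed to compare the mean LDL-C change between the two arms, assuming normally distributed data" (Section 7.2), with a "two-sided type I error rate of 0.05 to test the null hypothesis of no difference in LDL-C change between arms" (Section 5.1). VR-12 change scores are also compared by t-test (Section 7.4.3).

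For LDL-C, other rules can act before any imputation. Section 4.3.2 accepts a data-warehouse value when no study specimen is obtained. Section 6.1 accepts a chart value near 6 months, then a chart value from within the observation period, then the baseline value carried forward. The Section 6.1 substitutions are worded as options. Neither section says how they are ordered relative to Section 5.5.

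Section 3.2 allows for attrition as an upper limit: "Enrollment of 180 total participants will account for up to 20% loss to follow-up". It uses the same 20% limit to reach 244 participants (122 per arm).

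**The concern.** Filling a gap with the arm mean adds a record that has no deviation from that mean. The arm's sum of squares does not grow, but its sample size does. The variance is underestimated and then divided by too large an n, so the t-statistic is inflated on both counts. Nothing is gained in return: when the change score is imputed by its arm mean, the estimated difference is exactly the one from the observed participants. Median imputation has the same variance problem, and its point estimate need not equal the observed mean.

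At stake are the P value and interval of any between-arm test on which the option is used. They would look more precise than the data allow, even if the missingness were entirely random. Because the method is chosen after the outcome data have been reviewed, the plan does not protect against this.

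**Working it through.** **The plan's own figures.** Inputs from Section 3.2: difference 20 points, "a common standard deviation of 30"%, 80% power, two-sided 0.05. Per arm, n = 2(1.960 + 0.842)² × 30²/20² = 35.3, so 36 per arm and 72 in total, as stated. Doubling gives 144, and 144/0.8 = 180, as stated. For target attainment, 97/0.8 = 121.25, so 122 per arm and 244 in total, as stated.

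**Case A: the change score is imputed by its arm mean.** Let n be the number randomised per arm and m the number observed.
- Correct variance of an arm mean: s²/m.
- Reported variance: s²(m−1)/(n−1), divided by n.
- Ratio of reported to correct SE: √[(m−1)m / ((n−1)n)], about m/n.
- Type I error ≈ 2[1 − Φ(1.96 × ratio)].

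| Per arm | Missing | Observed | SE ratio | Type I error |
|---|---|---|---|---|
| 122 | 5% | 116 | 0.951 | 0.062 |
| 122 | 10% | 110 | 0.901 | 0.077 |
| 122 | 20% | 98 | 0.802 | 0.116 |
| 90 | 20% | 72 | 0.799 | 0.117 |

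For 98 of 122: √[(97 × 98)/(121 × 122)] = 0.802; 1.96 × 0.802 = 1.573; two-sided tail 0.116. Coverage of the 95% interval is 1 − 0.116, about 88%. Simulation (20,000 runs, 20% missing) gave 0.113 for mean imputation at both sizes. For median imputation it gave 0.118 (122 per arm) and 0.123 (90 per arm).

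**Case B: only the 6-month value is imputed, and the observed baseline is subtracted.** Assume equal SDs σ at the two times, correlation ρ between them, and p = m/n.
- Correct variance of the arm's mean change: σ²(1/m + 1/n − 2ρ/n) = (σ²/n)(1 + p − 2pρ)/p.
- Reported variance: observed changes have variance 2σ²(1−ρ) and imputed ones σ², so approximately (σ²/n)[2p(1−ρ) + (1−p)] = (σ²/n)(1 + p − 2pρ).
- The ratio of variances is p, so the SE ratio is √p whatever the value of ρ.

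At 98 of 122, √0.803 = 0.896; 1.96 × 0.896 = 1.757; type I error 0.079. At 110 of 122, √0.902 = 0.950; 1.96 × 0.950 = 1.861; type I error 0.063. Simulations with ρ from 0 to 0.9 gave 0.074 to 0.082 at 20% missing and 0.060 to 0.064 at 10%. In this case every baseline enters the estimate, so it is not the observed-participant estimate.

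**Valid alternatives in the same setting** (122 per arm, 20% missing, 3,000 simulations). Multiple imputation within arm, with 20 imputations and Rubin's rules, gave 0.052. Analysis of observed data gave 0.054. The simulation standard error is √(0.05 × 0.95/3000) = 0.004, so both are at the nominal level.

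**The case against.** The strongest reply is that Section 6.1 already governs missing LDL-C. A participant who misses the final blood draw may still have a chart value, and failing that the baseline can be carried forward. Loss to follow-up at the 20% limit is therefore not the same as 20% of primary outcomes being mean-imputed. Carry-forward has its own weaknesses (bias and attenuation) but not this one: with 20% of each arm carried forward, no mean change and equal random missingness, simulated type I error stayed at about 0.05. This stands, and it limits what can be said about the primary outcome. It does not remove the point: the fallbacks are optional, their order relative to Section 5.5 is unstated, and the survey outcomes have no equivalent.

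A second reply is that Section 5.5 is general and permissive. It speaks of partially observed outcomes, leaves the method to judgement, and cites one source on imputing VR-12 summary scores and two on multiple imputation. Section 7.5 also allows a complete-case replication. One could read the mean and median options as meant for missing questionnaire items. The wording does not confine them to items, and the PAM-13 already has its own prorating rule in Section 6.4.1. That the primary outcome is covered follows from the absence of any exemption; it is not stated.

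A reader might infer that the plan doubles the type I error of the primary test at its expected attrition. The document does not support that. The 20% is an upper limit, mean imputation is one of several options, and the figure of 0.116 requires that the change score itself be imputed.

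**Conclusion.** Wrong as written, in a limited sense: Section 5.5 lists as acceptable a method that does not hold the stated error rate when used with the plan's t-tests. If it is used, type I error at 122 per arm lies between about 0.06 and 0.12 for 10% to 20% missing, depending on the fraction missing and on which quantity is imputed. These figures assume normal data, missingness completely at random and equal between arms, and no variance correction. They isolate the variance error and leave out any bias from informative dropout. For LDL-C they apply only to values still missing after the Section 4.3.2 and 6.1 fallbacks, a number that the document does not let one predict. For VR-12 change scores they apply directly to whatever fraction is missing. The point merits a change because it affects error rates and is cheap to remove, not because the primary result is bound to be wrong.

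**What to change.** - In Section 5.5, delete mean and median imputation for any outcome tested between arms. Validated item-level scoring rules for questionnaires can stay.
- Name the method instead: multiple imputation within arm, with the baseline value of the outcome and any interim LDL-C in the model, a stated number of imputations, and Rubin's rules. Analysis of observed outcomes is an acceptable alternative. It should be defined outcome by outcome, since the complete case population in Section 4.4.2 also requires both surveys.
- State the order of steps for LDL-C: which Section 6.1 fallbacks are applied first, and which values then remain to be imputed. An interim LDL-C already used as the outcome under Section 6.1 should not also serve as a predictor for the same participant.

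Multiple imputation can be combined with the unadjusted comparison in Sections 5.1 and 7.2, so the primary test need not change. A baseline-adjusted model would be a larger step, because Section 7.1 plans no prespecified adjustment.

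The cost is a wording change, a little more analysis work, and somewhat wider intervals than single imputation would show. Data collection and sample size are unaffected.
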